MUSE Device to Improve Sleep Quality in Midlife Women

NCT05972486

31January2024

IRB Minimal Risk Protocol Template

General Study Information

Principal Investigator: [name], PA-C

Co- Principal Investigator: [name], DNP

Co- Investigator: [name]

Lead Coordinator: [name]

Study Title: MUSE Device to Improve Sleep Quality in Midlife Women

Protocol version number and date: V4 01/31/2024

Research Question and Aims

Hypothesis:

We hypothesize that the daily use of the Muse-S headband system will be an effective strategy for improving the sleep quality in peri- and postmenopausal women. We anticipate that the women who utilize the Muse-S headband will have improvements in time to sleep onset and sleep maintenance. We also anticipate a positive correlation between duration and frequency of use of the device and the improvement in sleep quality.

Aims, purpose, or objectives:

1. To obtain preliminary evidence regarding the feasibility of using the Muse-S headband system for management of sleep disturbances in peri- and postmenopausal women.
2. To obtain preliminary data on the effectiveness of the Muse-S headband system for management of sleep disturbances in peri- and postmenopausal women and to ascertain whether duration of treatment impacts efficacy.
3. To obtain preliminary data on the effectiveness of the Muse-S headband system in improving secondary outcomes of sleep quality including stress levels, mood and sexual function.

The overarching purpose of this study is to obtain preliminary evidence regarding the efficacy of the Muse-S headband system for management of sleep disturbances (insomnia and sleep disruption) in midlife women. This goal will be achieved with the following specific aims:

Objectives: The overarching goal of this project is to test the feasibility and efficacy of the Muse-S™ Headband, an electroencephalographic device, in management of sleep disturbances in midlife women.

Background:

Sleep problems (insomnia and sleep disruption) affect nearly half the women during the menopause transition and the postmenopausal years. The etiology of sleep disturbances in peri- and postmenopausal women is

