All study participants will receive a new Muse-S headband system at study entry and will be asked to utilize it daily for a minimum of 10 minutes day for a period of 6 months (24 weeks). Three of the seven sessions per week will specifically be asked to be mind meditation.

The participants will be provided instructions on setting up the device and connecting it to their smart device. They will also receive general education on the different features of the Muse-S Headband. They will have access to specific education on meditation. They will also have access to sleep tools on their app.

The participants will complete the ASCQ-Me Sleep Impact-Short Form, Epworth Sleepiness Scale and Sleep Quality Assessment PSQI for evaluation of their sleep. In addition they will also completed the the Patient Health Questionnaire (PHQ-9), Generalized Anxiety Disorder Scale (GAD-7), Female Sexual Function Index (FSFI) and Female Sexual Distress Scale (FSDS-R), Quality of Life- (LASA), Perceived Stress Scale (PSS) and Resilience- (CD-RS10). Quality of Life, mood, anxiety, stress and sexual function are often negatively impacted by poor sleep.

The weight, body mass index and blood pressure will be obtained from the MWSHC, Community Internal Medicine, Executive Health, or Family Medicine visit data at 0 and 6 months.

The data will be recorded in REDCap at baseline, 3 months, and 6 months.

All study participants will have access to The Muse-S™ Headband system's customer service team based in Toronto, Canada, by telephone and email for assistance should they experience technical problems with the device.

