Server Data: As the subject completes any Muse-S sessions, the information from these sessions will be uploaded to the Muse-S ICloud servers hosted by Google. Each subject will be able to see their own data at the end of each session, and data from the previous session stored in the "me" tab in the app. Subject to the study organizers ensuring that the subjects have signed the appropriate consents, study organizers will have access to each subject's data to monitor compliance, performance and outcomes, but will not get access to Journal entry information (if subject chooses to write a Journal entry). These data that the study organizers will have access to may include the study-specific identification number, gender, and age of the subject, the session type, the time and duration of each session, EEG data, heart rate (PPG) data, and the performance per session. Interaxon's privacy policy, which can be found at

██████████ will apply to Interaxon's use of the subjects' data. To maximize protection of the individual's privacy, the study organizers will ensure that the subjects are assigned anonymized email address and names for use in the Muse -SÔ application and when contacting the Muse-SÔ customer support. To ensure that no health data is shared with Interaxon, the study organizers have agreed to ensure that no health data will be shared with Interaxon. At the end of the study, the data collected in Google ICloud Server associated with study email addresses will be deleted.

Subject Retention

Participants will not be remunerated for participating in this study, but they will be allowed to keep the Muse-S headbands.

Study Design

We will use standardized procedures to ensure uniform instructions and support for all subjects for the recruitment, screening, and study entry.

Recruitment:

Women that come to the Menopause and Women's Sexual Health Clinic (MWSHC), Community Internal Medicine, Executive Health or Family Medicine at Mayo Clinic Rochester, who are identified as having significant sleep disturbance based on a standard questionnaire used for assessment of sleep quality and duration- the Pittsburgh Sleep Quality Index (PSQI) score >5 are recruited to the study based on the inclusion/exclusion criteria. If the participant is interested in the study the clinician will notify the study coordinator of participants eligibility, study coordinator at that time will set up a designated time to sign consent and get the participant enrolled in the study.

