Participants will not be reimbursed for their time spent in the study, but all participants will be given the option of keeping the Muse-S™ Headband system for continued use post study participation.

Consent and Screening:

Study coordinator will meet with the potential participant who has expressed an interest in participating in the study. They will begin by introducing the study details, and after determining that the subject has continued interest in study participation, will move on to the study consent. If the subject chooses to consent, they will screen the participant for study entry inclusion/exclusion criteria. If the study entry criteria are met, the subject will begin their study participation. They will be asked to complete the study questionnaires.

Please note: Participants must have access to an iOS or Android capable device to take part in this study in order to interact with the Muse-S™ Headband system.

Treatment phase:

During the first three months of study, participants will be asked to complete the intervention portion of the study using the Muse-S™ headband. If the MUSE device is not being used at least 3x a week for 10 minutes a day, the participant may get a reminder email or a phone call to remind them to use the Muse-S™ headband

system. Participants will receive an email link at 90 days from REDCap to complete their questionnaires for the study. If not completed in a timely manner there will be reminders by email and/or phone to complete.

Study Follow-Up Visit:

The study will consist of follow up at 3 month and 6 months.

3 month (questionnaire only visit): questionnaires will be sent via email **NOTE:** once questionnaires are complete the study coordinator will check the PHQ 9 score the same day the participant completes the questionnaire via the electronic link. The coordinator will immediately notify the investigators if the score is severe or subject indicates suicidal ideation. The investigators will contact the patient immediately (same day) and if there is concern for active suicidal thoughts, they will recommend the patient pursue emergency evaluation (such as local ED or 988 suicide prevention hotline) or contact local authorities for a welfare check if the patient declines. If severely depressed but no active thoughts of self-harm/plan, we will recommend an appointment with their PCP, EAP (if Mayo Employee) and offer the resource Psychology Today to help find a mental health provider.

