stress and sleep were taken. That information will be utilized to estimate the association between the average of time spent using the Muse-S with the stress and sleep level outcome. As secondary aim, the results of questionnaires for stress levels, mood and sexual function will be analyzed using the same linear mixed model with questionnaires being done at different intervals of the study to determine changes over time. Given the number of outcomes assessed, all analyses will be considered exploratory.

Endpoints:Primary Hypothesis:

- The regular use of the Muse headband will increase quality and quantity of sleep.

Secondary Hypothesis:

- The regular use of the Muse headband will decrease perceived stress levels, decrease anxiety, and improve sexual health.

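### The use–sleep model relates average Muse-S time, with no averaging window and no frequency term, to sleep level, whereas the hypothesis concerns duration and frequency of use and improvement in sleep

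*Combined protocol and SAP*

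**What the plan says.** - **Hypothesis:** "We also anticipate a positive correlation between duration and frequency of use of the device and the improvement in sleep quality". There are two exposures, and the outcome is improvement.
- **Data Analysis Plan:** frequency and duration of use are to be described and graphed over six months of treatment. A repeated-measures linear mixed model is then to estimate "the association between the average of time spent using the Muse-S with the stress and sleep level outcome". The same model is reused for the secondary questionnaires, there with the stated purpose of examining change across the study. All analyses are labelled exploratory.
- **Methods:** participants are asked to use the device "for a period of 6 months (24 weeks". On outcomes: "The data will be recorded in REDCap at baseline, 3 months, and 6 months".
- **Treatment phase:** "During the first three months of study, participants will be asked to complete the intervention portion of the study". The 3-month questionnaires go out at 90 days. A reminder may follow "If the MUSE device is not being used at least 3x a week for 10 minutes a day".
- **Server Data:** the data available to the study team may include "the session type, the time and duration of each session".

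**The concern.** The model sentence differs from the hypothesis in three ways.

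1. **Window.** No period or denominator is given for the average. The only period attached to use data nearby is six months, and such an average includes use that happened after the 3-month score. Sleep at three months cannot be a result of that use, but it may well influence it.
2. **Frequency.** It is hypothesised, then only described. No model relates it to sleep.
3. **Improvement.** The outcome is worded as a level. No change score, baseline covariate or use-by-time term is stated. If use is a plain main effect across all visits, the slope partly reflects how a woman slept before she had the device.

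The study has one arm, so this is the only planned analysis that ties use of the device to sleep.

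**Working it through.** The plan gives no figure for this analysis, so there is none to reproduce.

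**Window.** Inputs: 24 weeks (Methods) and the 90-day questionnaire (Treatment phase).
- 24 × 7 = 168 days; 168 − 90 = 78; 78/168 = 46%.
- With six months taken as 180 days: 90/180 = 50%.
- A deliberately extreme illustration: woman A uses the device 10 min/day for 90 days and stops (10 × 90 = 900 min). Woman B starts after day 90 at 900/78 = 11.5 min/day. Both average 900/168 = 5.4 min/day over 24 weeks, but their use before the 3-month score is 10 and 0 min/day.

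**Frequency.**
- Seven 10-minute sessions and two 35-minute sessions a week both total 70 min, or 10 min/day. The second pattern falls below the three-times-a-week reminder threshold.
- If the average is per session instead, 7 × 10 and 3 × 10 min a week both give 10 min, although daily use is 10.0 and 30/7 = 4.3 min.
- So neither denominator separates frequency from session length.

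**Weight of the pre-device visit, main-effect reading only.** Assume complete data, one fixed use value per woman, visit as a factor and no use-by-visit term. Let b0, b3 and b6 be the slopes of sleep on use at the three visits, and R the within-woman correlation matrix. The common slope is a weighted mean with weights R⁻¹1 / (1′R⁻¹1).
- Exchangeable R: weights 1/3, 1/3, 1/3.
- AR(1) with correlation 0.5: R⁻¹1 is proportional to (1, 1 − 0.5, 1) = (1, 0.5, 1), with sum 2.5. Weights are 0.40, 0.20, 0.40.
- If b0 = 0 and b3 = b6 = b, the slope is 2b/3 or 0.6b respectively.

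**Which correction addresses improvement?** Illustrative assumptions, not document values: score SD 3 (variance 9), within-woman correlation 0.5 (covariance 4.5), use scaled to SD 1, no true effect of use.
- *Use correlates 0.3 with the score at every visit* (covariance 0.3 × 3 = 0.9). Level slope: 0.9. Change slope: 0.9 − 0.9 = 0. Baseline-adjusted slope: (0.9 × 9 − 4.5 × 0.9)/(9 − 0.9²) = 4.05/8.19 = 0.49. In 1,500 simulated studies of 50 women, with the correlation at −0.3 or +0.3, the level model was significant at 5% in 77% or 76%, the baseline-adjusted model in 34%, and change in 5%. If the 0.3 is instead with an underlying stable sleep trait, the figures are 45–46%, 17–20% and 4–6%.
- *Use correlates 0.3 with the measured baseline score only* (follow-up covariance 0.5 × 0.9 = 0.45). Change slope: 0.45 − 0.9 = −0.45, a false improvement, since higher PSQI is worse. Baseline-adjusted slope: (0.45 × 9 − 4.5 × 0.9)/8.19 = 0.

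Each analysis is protected against one link between use and pre-device sleep and exposed to the other.

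**The case against.** The best defence is that the text can be read more favourably. The repeated measures cover each time point at which sleep was taken, so baseline is in the data. The plan speaks of change when it reuses the same model, which suits a use-by-time reading, and on that reading the baseline point largely falls away. The six-month phrase belongs to the descriptive statistics, so an average specific to each time point is also compatible with the text. Frequency appears in a single hypothesis sentence while Aim 2 asks about duration, and a daily average that counts non-use days as zero partly reflects frequency. Entry requires a motivation score of at least 5 and reminders may be sent, so a woman with no use for 90 days is unlikely. Everything is exploratory.

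Much of this stands. A reader might infer that the plan ignores baseline sleep, or that its estimate will be cut to two thirds. The documents support neither: the change reading is open, and with no covariance structure named there is no single dilution figure. Nor is 46% a bias; it is the share of calendar days that could be misplaced. A reader might also infer that adding baseline as a covariate would settle the matter; the calculation above shows that it may not.

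The defence does not supply what is missing. The favourable readings are possible but not written, and no reading adds a frequency exposure. The exploratory label limits what may be claimed, not what the coefficient measures.

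**Conclusion.** The concern holds as a mismatch between hypothesis and model that should be corrected. Three parts rest on different ground:

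- **Frequency:** the model has no term for it, whichever way the model is read.
- **Window:** none is stated. The 46% (or 50%) applies only if the six-month use data feed the model; its effect on the estimate cannot be sized from the documents.
- **Improvement:** no term is stated. The one-third or 40% weight on pre-device sleep applies only if use is a main effect on level at all three visits, and only under the covariance named with it.

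The consequence is moderate: no stated decision depends on this coefficient, but as written the analysis may not answer the study's own question about use.

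**What to change.** First reconcile the Methods and Data Analysis Plan (six months) with the Treatment phase (intervention portion in the first three months); the window cannot be fixed until then. Then amend the Data Analysis Plan:

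1. For each 3- and 6-month score, define duration as Muse-S minutes logged from device start to the date of that score, divided by the days in that period, with non-use days counted as 0.
2. Add sessions per week over the same window as a frequency exposure in its own model. Note that it overlaps with total time and that the two are not fully separated.
3. Make improvement the explicit target, through a use-by-time term or change from baseline on the same scale. Report the baseline-adjusted model alongside, and say that each handles a different link between use and pre-device sleep.
4. State that the association is observational and that reverse causation may remain.

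This should need no new data collection, provided the session times and durations that the Server Data section says may be available are supplied. The cost is drafting, analysis time and a few more exploratory models in 50 women.

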- Moderate to severe vasomotor symptoms warranting prescription medication use. The FDA categories for hot flash severity are classified as mild (sensation of heat without sweating), moderate (sensation of heat with sweating, able to continue activity), or severe (sensation of heat with sweating cause cessation of activity).
- Use of hormone therapy or hypnotic agents
- Use of supplements known to affect sleep
- A known, active, untreated clinically significant psychiatric condition
- Use of an investigational drug within 30 days of study enrollment or presence of a known history of any condition or factor judged by the investigator to preclude participation in the study or which might hinder adherence.
- Currently (within the past 3 weeks) been practicing mindfulness training on a weekly/regular basis

Potentially eligible participants will be identified from the MWSHC, Community Internal Medicine, Executive Health, or Family Medicine, where midlife women are evaluated for menopause and sexual health-related concerns. All the women seen in these areas will complete multiple questionnaires as part of their clinical evaluation, including the PSQI. They also complete questionnaires assessing mood (Patient Health Questionnaire 9, PHQ-9), anxiety (Generalized Anxiety Disorder 7, GAD-7), and sexual function (Female Sexual Function Index, FSFI and the Female Sexual Distress Score-Revised, FSDS-R), Quality of Life-LASA), Perceived Stress Scale (PSS) and Resilience- (CD-RS10).

Review of medical records, images, specimens

- The study involves data that exist at the time of IRB submission and data that will be generated after IRB submission. Include this activity in the Methods section.

Data Analysis**Data Analysis Plan:**

Demographic characteristics are described using mean and standard deviations or frequencies and percentages based on the type of variable. For the primary aims being the feasibility and efficacy of the MUSE device, descriptive statistics and graphical displays will be presented for data obtained on frequency and duration of use over the treatment time of six months. A linear mixed model with repeated measures for each time point that

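### Use is analysed as undivided Muse-S time; a split by logged session type, placed beside total use, would separate meditation from tool use that may follow poor sleep

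*Combined protocol and SAP*

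**What the plan says.** The hypothesis (Research Question and Aims) concerns the device as a whole: "We also anticipate a positive correlation between duration and frequency of use of the device and the improvement in sleep quality".

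Study Design and Methods, Methods, requests daily use of at least 10 minutes for six months. On content it says "Three of the seven sessions per week will specifically be asked to be mind meditation". It does not say what the other four sessions should be, and it adds: "They will also have access to sleep tools on their app".

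Server Data lists what study staff may be able to see, including "the session type, the time and duration of each session, EEG data".

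Under Treatment phase, a participant may be sent a reminder "If the MUSE device is not being used at least 3x a week for 10 minutes a day". Session type is not mentioned.

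The Data Analysis Plan describes "frequency and duration of use over the treatment time of six months" for feasibility. It then uses a repeated-measures linear mixed model to estimate the association of "the average of time spent using the Muse-S with the stress and sleep level outcome". Neither part refers to session type. The plan labels every analysis exploratory.

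**The concern.** The Background rests the case for the device on EEG feedback that reinforces meditation. The Methods then allow a mixture of activities, and the analysis adds their time together. Sleep-tool time may behave differently from meditation time. Every participant enters as a poor sleeper, and a woman lying awake may run a sleep tool longer or more often. If that time is in the total, part of the exposure is a consequence of the outcome.

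Two results are at stake. The first is the use-sleep coefficient. In a single-arm study it is one of the few internal sources of evidence on whether use matters, and in pooled form it cannot separate practice from sleep-driven tool use. The second is the feasibility summary, which could show good use with few or none of the requested meditation sessions.

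**Working it through.** **Figures from the documents.** Requested use is 7 × 10 = 70 minutes a week at the minimum. Requested meditation is 3 × 10 = 30 minutes, so the share is 30/70 = 43%. The reminder threshold is also 3 × 10 = 30 minutes a week, and three sessions with no meditation would meet it. If the other four sessions lasted 30 minutes each (an assumption), the meditation share would be 30/(30 + 120) = 20%.

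**Inputs the documents do not give.** They state no minutes, SDs or correlations for any session type, and no power basis for the 50 women. What follows is an illustration on assumed values, and a cross-sectional simplification of the mixed model.

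**Formula.** Let M be meditation time and S sleep-tool time, with k = SD(S)/SD(M). Let r_m and r_s be their correlations with sleep improvement, and ρ the correlation between M and S. The correlation of total time with improvement is

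r_total = (r_m + k·r_s) / √(1 + k² + 2kρ).

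ρ = 0 if the two kinds of time are independent. ρ = r_s·r_m if tool use simply follows the outcome. With r_m = 0.40:

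| Assumed tool-time relation | k = 0.5 | k = 1 | k = 2 | k = 4 |
|---|---|---|---|---|
| r_s = 0 (unrelated) | 0.36 | 0.28 | 0.18 | 0.10 |
| r_s = -0.15, follows outcome | 0.30 | 0.18 | 0.05 | -0.05 |
| r_s = -0.3, follows outcome | 0.24 | 0.08 | -0.09 | -0.20 |
| r_s = +0.3 (tools help), ρ = 0 | 0.49 | 0.49 | 0.45 | 0.39 |

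Example, third row, k = 2: (0.40 - 0.60)/√(1 + 4 - 0.48) = -0.20/2.126 = -0.09.

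**When the sign changes.** The numerator is negative only if k > r_m/|r_s|. That is 0.40/0.3 = 1.33 at r_s = -0.3, and 0.40/0.15 = 2.67 at r_s = -0.15.

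**What this means at n = 50.** In a simulation (20,000 runs per scenario, Fisher z, two-sided 0.05), meditation time analysed alone gave a significant positive result in 83-84% of runs. Pooled time with r_s = -0.3 did so in 38%, 7%, 0.5% and 0% for k = 0.5, 1, 2 and 4, and gave a significant negative result in 29% at k = 4. Unrelated tool time (r_s = 0) gave 74%, 52%, 24% and 10%. For scale, 50 women give 80% power for a correlation of about 0.39.

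**Does entering both exposures help?** With r_s = -0.3 following the outcome, ρ = -0.3 × 0.40 = -0.12. The partial correlation of M with improvement given S is (0.40 - (-0.12)(-0.3))/√((1 - 0.0144)(1 - 0.09)) = 0.364/0.947 = 0.38, whatever k is. That is close to 0.40, where the pooled value runs from 0.24 to -0.20.

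**The case against.** The strongest reply is that the plan analyses what it hypothesises. The hypotheses name use of the device, and the Methods describe daily use of the whole system with its features. Total time is therefore a legitimate exposure, and replacing it with meditation time would discard up to four of the seven requested sessions. This stands. A reader might infer that the plan uses the wrong exposure, but the documents do not support that. The split belongs beside total time.

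A reader might also take it as established that sleep-tool time is in the total. The documents say only that the tools are available on the app. They do not say that the tools need the headband, are logged as sessions, or count toward the seven. Pooling is inferred from silence, and session type is listed only as something the accessible data may include.

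The reversal is also conditional. At r_s = -0.3 with k of 0.5 or 1 the pooled correlation stays positive, and if the tools help, pooling costs little or nothing. No figure in the documents shows which case applies.

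The reminder is a discretionary prompt. It is not an adherence definition, and the documents classify no one as a user or non-user. What remains is that it does not say which session types it counts, although the Methods request meditation in particular.

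Finally, meditation time can respond to sleep too: poor sleepers may practise more, or stop when they see no benefit. The split does not cure that.

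**Conclusion.** The point holds as an inexpensive improvement, not as an error that invalidates the plan. As written, the feasibility summary could show good use with none of the requested meditation, and the use-sleep coefficient could not separate meditation from sleep-driven tool use. Both statements depend on tool sessions being logged as Muse-S time.

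Dilution then needs only tool time that varies between women for reasons unrelated to improvement. A change of sign needs two further conditions: greater tool use by women who sleep badly, and an SD ratio above r_m/|r_s|, which is 1.33 at the assumed 0.40 and -0.3. It is a possibility, not a prediction. The exploratory status of a 50-woman, single-arm study limits the weight of the point, but preliminary evidence still has to be interpretable.

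**What to change.** 1. Keep total device time as the exposure that matches the hypothesis.
2. Beside it, prespecify a model with meditation time and other-session time (including sleep tools) as separate exposures. Measure each over the interval before the questionnaire (baseline to month 3, month 3 to month 6) and adjust for baseline PSQI. State that sleep-tool time is not interpreted as dose.
3. In the feasibility summary, report the share of woman-weeks with the three requested meditation sessions next to total frequency and duration of use.
4. Reconcile Methods and Treatment phase by stating which session types the reminder counts.
5. Confirm that the server export labels session type and whether sleep-tool sessions appear in it. The split depends on this.
6. Say in the plan that the split lessens outcome-driven use but does not remove it, and that the analysis remains exploratory.

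The cost is a few lines of analysis text, one more exposure variable in a small data set, and a headline use figure that may look lower. No new data collection appears necessary if session type is delivered as Server Data anticipates.
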